#### **9.7.3.2               Secondary Effectiveness Endpoints**

The secondary effectiveness endpoints are:

- The percentage of patients with virological response (HCV RNA  $<50$  IU/mL) at EoT
- The percentage of patients with relapse (defined as HCV RNA  $<50$  IU/mL at EoT followed by HCV RNA  $\geq 50$  IU/mL)

---

Confidential Information

No use or disclose outside AbbVie is permitted without prior written authorization from AbbVie  
The Netherlands v 1.4 (26 March 2018). Protocol based on AbbVie shell protocol version 3.0 (22 April 2015) Page 36 of 65

- The percentage of patients with breakthrough (defined as at least one documented HCV RNA <50 IU/mL followed by HCV RNA ≥50 IU/mL during treatment).
- The number and percentage of patients meeting each and any of the following SVR12 non-response categories:
  - On-treatment virologic failure (breakthrough [defined as above ] or failure to suppress [each measured on-treatment HCV RNA value ≥50 IU/mL])
  - Relapse (defined as HCV RNA <50 IU/mL at EoT or at the last on-treatment HCV RNA measurement followed by HCV RNA ≥50 IU/mL post-treatment)
  - Premature study drug discontinuation with no on-treatment virologic failure
  - Missing SVR12 data and/or none of the above criteria

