### **9.9                   Limitations of the Research Methods**

The limitations of observational studies, such as uncontrolled confounding by lack of randomization, and difficulties to clearly interpret treatment effects in the context of missing data are well known. Their validity can be increased by accurate outcome measurements, documentation of the most common confounders, sufficient length of follow-up and by activities to obtain complete recording of available data as well as by searches for missing key data.

The most important outcome measure in this study is HCV RNA. Missing or unrecorded follow-up HCV RNA data can in particular lead to an underestimation of the real SVR rate as compared to the SVR rate of interventional trials. Highly sensitive and quantitative diagnostic tests are required to measure HCV RNA levels in blood. In an observational

---

Confidential Information

No use or disclose outside AbbVie is permitted without prior written authorization from AbbVie

The Netherlands v 1.4 (26 March 2018). Protocol based on AbbVie shell protocol version 3.0 (22 April 2015) Page 41 of 65

---

study each center will be using its own test – either commercially available or so-called “home-brew” tests – which might change from one visit to the next within a patient data set. The challenge is to accurately and consistently document test properties such as the LLoD and the LLoQ to put the results into perspective of prior outcomes from randomized controlled trials with (usually) central laboratory assessments for all trial participants.

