4.2.7.2 Secondary Variables

4.2.7.2.1 Secondary Effectiveness Variables

Response

For the other response rates (i.e. SVR24, EoT response rate, relapse rate, viral breakthrough), the simple percentage of patients and a two-sided 95% confidence interval (CI) of the percentage will be computed (based on the Wilson's score method) as well. The EoT response rates will be reported for CP and the SVR24 rates will be reported for the respective CPSFU, stratified by genotype and cirrhosis status and overall. The relapse rates will be estimated stratified by SVR window (i.e. during SVR12 window=relapse₁₂, during SVR24 window=relapse₂₄, after SVR24

window=relapse_{late}) and stratified by genotype and cirrhosis status and overall in patients of the CP with EoT response who fulfilled the following criteria:

- completed treatment as defined previously,
- had at least one HCV RNA measurement ≥ 70 days post-treatment or was a treatment failure between EoT and 70 days post-treatment.

Viral breakthrough rates [defined as at least one documented HCV RNA <50 IU/mL followed by HCV RNA ≥ 50 IU/mL during treatment] will be estimated overall and stratified by genotype and cirrhosis status in all patients of the CP, who have at least one undetectable or unquantifiable, on-treatment HCV RNA measurement and at least one on-treatment or EoT measurement thereafter.

Non-Response

In another table, the numbers and the percentages of the SVR12 non-responder categories and responder will be summarized for CP patients, overall and stratified by genotype and cirrhosis status. The following SVR12 non-response categories will be considered:

- On-treatment virologic failure (breakthrough [defined as at least one documented HCV RNA <50 IU/mL followed by HCV RNA ≥ 50 IU/mL during treatment] or failure to suppress [each measured on-treatment HCV RNA value ≥ 50 IU/mL])
- Relapse (defined as HCV RNA <50 IU/mL at EoT followed by HCV RNA ≥ 50 IU/mL post-treatment and completed treatment as defined previously)
- Death and none of the above
- Premature study drug discontinuation with no on-treatment virologic failure and none of the above
- Insufficient virological response, other than those mentioned above (patients for whom insufficient virological response was reported, or who had HCV RNA ≥ 50 IU/mL post EoT) and none of the above
- Missing SVR12 data and/or none of the above criteria

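### Viral breakthrough rests on one unconfirmed value of 50 IU/mL or more, so re-suppressed patients are counted, and the non-response categories are only partly ordered

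*SAP*

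**What the plan says.** **Definition.** Protocol section 9.7.3.2 lists "The percentage of patients with breakthrough (defined as at least one documented HCV RNA <50 IU/mL followed by HCV RNA" at or above 50 IU/mL on treatment. SAP section 4.1.2 repeats this, and SAP section 4.2.7.2.1 uses the same rule for the rate: "Viral breakthrough rates [defined as at least one documented HCV RNA <50 IU/mL followed by HCV RNA ≥ 50 IU/mL during treatment". The SAP denominator is the core-population patients "who have at least one undetectable or unquantifiable, on-treatment HCV RNA measurement and at least one on-treatment or EoT measurement thereafter".

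**Categories of SVR12 non-response.** The list in SAP section 4.2.7.2.1 opens with "On-treatment virologic failure (breakthrough [defined as at least one documented HCV RNA <50 IU/mL followed by HCV RNA ≥ 50 IU/mL during treatment"; this first category also takes in patients who were never suppressed on treatment. Relapse is second: below 50 at end of treatment (EoT), then 50 or more "post-treatment and completed treatment as defined previously". Third is "Death and none of the above". Premature discontinuation follows and requires that there was no on-treatment virologic failure. Then come other insufficient virological response and, last, missing SVR12 data, joined by and/or to none of the earlier criteria. SAP section 4.1.2 has a shorter list, without death or insufficient response, and counts patients who meet each and any of the categories.

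**Measurements.** Protocol section 9.9 says that each centre uses its own HCV RNA test, "which might change from one visit to the next within a patient data set". SAP section 4.2.2 leaves all HCV RNA testing to the physician. The imputation rules in protocol section 9.7.1 and SAP section 4.2.3 fill missing values only.

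**The concern.** The definition looks only at whether a value of 50 or more ever follows a value below 50 during treatment. It does not ask whether the rise was confirmed, whether it persisted, or what came next. Because imputation never overrides an observed value, later negative results cannot cancel it.

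The protocol describes local tests that can change between visits, so an isolated value just above 50 is a foreseeable event, although the documents do not say how often it occurs. At stake are the breakthrough rate and the recorded reason for failure. Both rest on very few patients in a study of 50 to 55, so one patient is visible in the tables.

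**Working it through.** There is no planned figure to reproduce. SAP section 3.2 says the sample size has no statistical basis, and no breakthrough rate is assumed.

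**Step 1. Apply the written rules to example sequences.** Values run in time order.

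| Case | Sequence | Breakthrough rate | EoT response | SVR12 | Non-response table |
|---|---|---|---|---|---|
| A | <50, ≥50, EoT <50, SVR12 <50 | counted | yes | yes | responder |
| B | <50, ≥50, EoT <50, treatment completed, ≥50 in the SVR12 window | counted | yes | no | meets on-treatment failure and relapse |
| C | <50, EoT ≥50, SVR12 <50 | counted | no | yes | responder |
| D | <50, ≥50, <50, then death, no SVR12 value | counted | depends on timing | no (missing counts as failure) | on-treatment failure; death category closed |
| E | <50, ≥50, <50, stopped early, no SVR12 value | counted | depends on timing | no | on-treatment failure; discontinuation category closed |
| F | <50, ≥50, EoT <50, then lost to follow-up | counted | yes | no | on-treatment failure, and possibly missing as well |

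In D and E the precedence is written: death carries a none-of-the-above clause, and discontinuation excludes on-treatment failure. In B it is not written, because relapse has no such clause. In F the and/or leaves it open.

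**Step 2. Size per patient.** With x counted patients among n, p = x/n and z = 1.96, the Wilson limits are

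[p + z²/(2n) ± z·√(p(1−p)/n + z²/(4n²))] / (1 + z²/n).

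For x = 1, n = 50: the centre is (0.02 + 0.0384)/1.0768 = 0.0542 and the half-width is 1.96·√(0.000392 + 0.000384)/1.0768 = 0.0507. For x = 0 the upper limit reduces to z²/(n + z²) = 3.84/53.84 = 0.0713.

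| | n = 50 | n = 55 |
|---|---|---|
| One re-suppressed patient counted | 2.0% (0.35 to 10.50) | 1.8% (0.32 to 9.61) |
| Same patient not counted | 0% (0 to 7.13) | 0% (0 to 6.53) |

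This takes every enrolled patient as evaluable. A smaller denominator makes the step larger: in an assumed stratum of 10, one patient is 10%.

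**Step 3. How many to expect.** The documents give no frequency for isolated values. Assume a per-test probability q of 0.1% to 2% and k = 1 to 3 later tests per patient. The expected number is n(1 − (1 − q)^k), and the chance of at least one is 1 − (1 − q)^(nk).

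- Lowest: q = 0.1%, k = 1, n = 50 gives 0.05 patients.
- Middle: q = 0.5%, k = 2 gives 0.50 (n = 50) to 0.55 (n = 55), with a 39% to 42% chance of at least one.
- Highest: q = 2%, k = 3, n = 55 gives 3.2 patients.

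**The case against.** The definition is the protocol's own choice, and the SAP repeats it faithfully. It is transparent and can only raise the breakthrough count. Testing is discretionary, so a confirming sample may not exist. Different and changing assays do not prove that values cross 50 by assay alone, and SAP section 4.2.3 sets a common rule for reading undetectable and unquantifiable results. Case A needs three samples by EoT, while the SAP's HCV RNA windows after baseline and up to EoT are only week 4 and EoT. The table shells in Part II of the SAP are not among the documents at hand and may fix the counting rule.

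Most of this limits likelihood and size. It does not close the gap. Case C needs only two on-treatment samples, and the definition speaks of documented values, not windows. A rule that uses the next value where one exists, and otherwise keeps the single value, also meets the point about missing confirmation.

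Three stronger readings are tempting and not supported:

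- *A relapse is moved into on-treatment failure.* The list order hints at this, but the none-of-the-above wording starts only at death and SAP section 4.1.2 says each and any. As written, the patient meets both categories and also stays in the separate relapse rate.
- *Missing SVR12 data are refiled as virologic failure.* The and/or wording may keep the patient in the missing category too.
- *The tables contradict each other.* The breakthrough, relapse and non-response outputs have separately stated denominators. A patient who appears in several of them is overlap.

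**Conclusion.** The point holds as a gap in a secondary definition. One unconfirmed value of 50 or more makes a patient a viral breakthrough whatever follows. For SVR12 non-responders it also takes priority over death and premature discontinuation, while its relation to relapse, and possibly to missing data, is left undefined. Two programmers could therefore produce different non-response tables from the same data.

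The size is about 2 percentage points per patient in a descriptive rate, if all 50 to 55 patients are evaluable. The number of such patients is unknown; the range in the check rests on assumed test error rates. SVR12 is unchanged, and a cured patient is affected only in the breakthrough rate.

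A reader might also infer that one patient would alter a third or more of all failures. The documents do not fix that share. Protocol Table 1 cites SVR12 of 90% to 100% in non-cirrhotic genotype 1 patients. At 90%, 50 patients give 5 failures, of which one is 20%, and missing SVR12 data counted as failure would add to the total.

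**What to change.** In SAP sections 4.1.2 and 4.2.7.2.1:

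1. Count breakthrough when a value of 50 IU/mL or more after a value below 50 is followed by another value of 50 or more at the next available HCV RNA, on or after treatment and before any new HCV therapy, or when no later value exists. The next value has to be allowed to fall after treatment. A rule that accepted the last value up to EoT would still count case C, a cured patient.
2. List patients whose next value is below 50 separately as transient.
3. Make the non-response categories mutually exclusive by stating the order in full, including relapse and missing data, and align the two SAP lists. Classify transient patients by their EoT and post-treatment outcome: relapse, death, discontinuation, other insufficient response, or missing.
4. Give the count under the protocol definition in a footnote.

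The cost is SAP wording and a small programming change on data already collected. The downside is a small departure from the protocol wording; the SAP already declares others, such as the upper bound on the SVR12 window. One ambiguity remains: if the next value after an on-treatment rise is a positive post-treatment sample, a lasting breakthrough cannot be told from a transient rise followed by relapse. The rule counts it as breakthrough, and the listing should show it.

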4.2.2 Definition of Baseline and Visit Time Windows

This observational study covers three documentation periods, see Figure 1. An overview of data to be collected throughout the study is summarized in Table 1.

Table 1 - Data Documentation Schedule

Assessment/ Procedure (only available data to be collected; no diagnostic or monitoring procedures to be applied to the patients apart from those of routine clinical practice)	Baseline	Treatment Period			Post-treatment (PT) Period		
		On-treatment visits	Mid treatment visit for pts receiving 24 weeks of therapy	EoT ^b	Early PT visit	SVR 12 visit	SVR 24 visit
Informed Consent	X ^a						
Demographic information	X						
IL28B	X						
Relevant CHC disease characteristics	X						
Liver fibrosis stage	X						
CHC treatment history	X						
HCV genotype and subtype	X						
HCV RNA samples	X	X	X	X	X	X	X
Clinical chemistry and hematology	X	X	X	X	X	X	X
ABBVIE REGIMEN initiation documentation	X						
ABBVIE REGIMEN adherence		X	X	X			
Concomitant medication	X	X	X	X			
Relevant medical history, co-morbidities	X						
sAE, AE and pregnancy reporting	X	X	X	X	X ^c	X ^d	X ^d
For patients receiving RBV: Evidence, in accordance with local label, that female patient or female partner of male patient is not pregnant	X						
Patient questionnaires – WPAI, EQ5D-5L	X			X		X	X
Health care resource utilization	X	X	X	X			

Abbreviations: EoT = End of Treatment (at Week 12 or 24 or at premature discontinuation),

PT = Post-Treatment

a Written informed consent must be obtained before any data documentation in the eCRF

b Patients who prematurely discontinue should return to the site to document EoT data

c Tolerability documentation until PT week 4

d Pregnancy reporting for patients treated with DAA +/- RBV

In accordance with the non-interventional nature of the study all HCV RNA measurements will be performed at the sole discretion of the physician and all HCV RNA measurements have to be entered into the eCRF. All recorded HCV RNA values will be assigned to appropriate time points (baseline, on-treatment visits, EoT visit, post-treatment visits) as follows:

Table 2 - Analysis Time Windows for HCV RNA

Phase	Time point	Time Window
Pre-Treatment	Baseline	Last value prior to start of study treatment (i.e. \leq study day 1)
On-treatment		Study day during treatment period ^{^#} (Study day 1 = first treatment day)
Treatment Week	4 (RVR*)	15 - 42 [^]

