4.2.3 Handling of missing data

No data will be imputed for any effectiveness or safety analyses except for the analyses of the HCV RNA endpoints and certain PRO endpoints. The discussion of missing data imputation for the PRO endpoints is included in section 4.2.7.2.2.

HCV RNA values will be selected for an RVR, EOTR and SVR analysis based on visit windows as defined in Table 2. When there is no HCV RNA value in a visit window based on defined visit windows, the closest values before and after the window, regardless of the value chosen for the subsequent and preceding window, will be used for the flanking imputation described below. For

analysis of RVR, EOT and SVR, if a subject has a missing HCV RNA value at a post-Day 1 visit but with undetectable or unquantifiable (LLoD or LLoQ \leq 50 IU/mL) HCV RNA levels at both the preceding value and succeeding value, the HCV RNA level will be considered undetectable or unquantifiable, respectively, at this visit for this subject. In addition, if a subject has an unquantifiable HCV RNA level at the preceding value and an undetectable HCV RNA level at the succeeding value, or vice versa, the HCV RNA level will be imputed as unquantifiable at this visit for this subject.

For analyses of RVR, subjects still missing a value for the visit after flanking imputation will be considered as a failure. For EoTR and SVR analysis, if there is no value in the appropriate window after flanking imputation but there is an HCV RNA value after the window, then it will be imputed into the EoTR or SVR window respectively. Subsequent to this flanking and backward imputation, if the HCV RNA value remains missing at a specific time point, then the subject will be considered as virological failure at this time point (i.e., not undetectable or unquantifiable).

If a subject starts another treatment for HCV, then all HCV RNA values for this subject measured on or after the start date of the new HCV treatment will be excluded from analyses. The subject will be considered a failure for summaries of viral response at all time points after the start of the new HCV treatment.

Due to the non-interventional nature of this study several different methods for determination of the HCV RNA value can be applied. For the purpose of the statistical analysis, a HCV RNA measurement is considered <50 IU/mL,

- if a PCR test was used

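### Failure to suppress has no minimum time on treatment, so an SVR12 non-responder sampled only on days 2-14 is labelled an on-treatment virologic failure

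*SAP*

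**What the plan says.** Protocol 9.7.3.2 and SAP 4.1.2 and 4.2.7.2.1 share one definition. On-treatment virologic failure is either breakthrough or, in the SAP's words, "failure to suppress [each measured on-treatment HCV RNA value ≥ 50 IU/mL". None of the three places gives a minimum exposure, an earliest study day or a minimum number of samples.

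SAP Table 2 (4.2.2) heads the on-treatment phase "Study day during treatment period", with day 1 as the first treatment day. Its footnotes admit values from study day 2 and up to 7 days after the last dose. The only scheduled on-treatment efficacy window before end of treatment (EoT) is Week 4, days 15-42. It serves rapid virological response and is not mentioned in the failure-to-suppress definition. Timing is otherwise open, because "all HCV RNA measurements will be performed at the sole discretion of the physician".

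In SAP 4.2.7.2.1, "the numbers and the percentages of the SVR12 non-responder categories and responder will be summarized for CP patients". On-treatment virologic failure is the first reason listed. Further down are death (if nothing above applies), "Premature study drug discontinuation with no on-treatment virologic failure and none of the above", other insufficient response and, last, "Missing SVR12 data and/or none of the above criteria".

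**The concern.** The table explains why patients did not reach SVR12, and above all whether the virus or something else was responsible. A value still at or above 50 IU/mL in the first two weeks says little about whether the regimen would have suppressed the virus. Under the rule, however, a single such value is enough for the virologic label, and that label then shuts the patient out of the death and discontinuation rows.

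The SAP's own structure points to a minimum. It calls suppression in the Week 4 window rapid, and it does not open an on-treatment efficacy window before day 15. For relapse it already adds an exposure condition that the protocol lacks: treatment completed, not shortened by more than 7 days. Failure to suppress has no such guard.

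The protocol (7.1) notes that earlier protease inhibitors did worse than expected in routine care, especially on tolerability. In a cohort this small, one patient in the wrong row can change how that question appears to be answered.

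**Working it through.** The plan gives no figure to reproduce, so the check is to follow the rule literally and then measure the weight of one patient.

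**Inputs**
- The failure-to-suppress definition and the order of categories: SAP 4.2.7.2.1.
- On-treatment values start on study day 2: SAP Table 2 footnote.
- Missing SVR12: "if the HCV RNA value remains missing at a specific time point, then the subject will be considered as virological failure" (SAP 4.2.3), so such patients do enter the table.
- Expected enrolment of 50-55 (SAP 3.2), an upper limit for the core population (CP).

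**Step 1: hypothetical SVR12 non-responders.** Patients A to D have no HCV RNA value after the one shown, so no flanking or backward imputation applies. The last column adds a requirement that the latest on-treatment value falls on or after a minimum day. Days 15, 29 and 42 were tried and gave the same result.

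| Patient | As written | With a minimum day |
|---|---|---|
| A: adverse-event stop on day 5; 5,000 IU/mL on day 5 | On-treatment virologic failure | Premature discontinuation |
| B: completer; 800 IU/mL on day 8 | On-treatment virologic failure | Missing SVR12 |
| C: death on day 10; 900 IU/mL on day 7 | On-treatment virologic failure | Death |
| D: stopped early; value on day 1 only (baseline) | Premature discontinuation | Premature discontinuation |
| E: at least 50 IU/mL on days 8, 29, 57 and 84 | On-treatment virologic failure | On-treatment virologic failure |

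A, B and C change row, while the true non-suppressor E does not. All five remain SVR12 non-responders either way. The last category is worded with and/or, so a loose reading could count B under missing as well, but B would still carry the virologic label.

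**Step 2: weight of one patient.** With p = x/n and k = 1.96, the Wilson limits are [p + k²/(2n) ± k√(p(1−p)/n + k²/(4n²))] / (1 + k²/n).
- 0/50: upper limit k²/(n + k²) = 3.8416/53.8416 = 7.1%.
- 1/50: centre (0.02 + 0.0384)/1.0768 = 0.0542; half-width 1.96 × √0.000776/1.0768 = 0.0507. The result is 2.0% (0.4-10.5%).
- 0/55: 0% (0-6.5%). 1/55: 1.8% (0.3-9.6%).
- In a genotype-by-cirrhosis stratum of 10 (assumed size): 0% (0-27.8%) against 10% (1.8-40.4%).

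The SAP plans counts and percentages for this table; the intervals are added here only to show scale.

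**Step 3: share of the reasons.** If 2 to 8 of 50 patients are non-responders (assumption: SVR12 of 96% to 84%), and if one such patient exists, that patient is 1/8 = 12.5% to 1/2 = 50% of all reasons listed.

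**The case against.** **Stop reasons appear elsewhere.** SAP 4.2.5 tabulates the main reason for early termination in the CP and the safety population, with adverse events, virological non-response and loss to follow-up kept apart. Table 11 lists adverse events leading to withdrawal, and the non-response table is repeated for treatment completers. So a reader might infer that tolerability stops vanish from the report, and they do not. But none of these outputs corrects the main CP table. The completers' version keeps patient B, and the stop-reason table could show an adverse-event stop for someone the non-response table calls a virologic failure.

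**The early value can already count as EoT non-response.** The EoT window reaches back 28 days from the last dose, so A's value falls inside it. That is true, but EoT response is a rate. It does not say why the patient failed, and B's day-8 value lies outside the window for a 12- or 24-week course.

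**The clinical premise is not quantified.** From the SAP's baseline cut-offs, reaching 50 IU/mL takes a fall of log10(400,000/50) = 3.9 to log10(10,000,000/50) = 5.3. That is a distance, not a time, and the documents give no rate of decline. The support within the documents is the day-15 opening of the first efficacy window.

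**Such patients may be rare.** The documents anticipate regular follow-up, and the patient must be a non-responder with early values only. This stands: the frequency cannot be derived, and nothing supports calling these patients typical. A completer with an early value and a positive post-treatment value would in any case only move to other insufficient response, which is still a virologic row.

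**Conclusion.** The point holds as a defect of definition. Followed exactly, the rule gives the wrong reason to an SVR12 non-responder sampled only on days 2-14. One such patient moves the on-treatment virologic failure row from 0% to about 2% of a CP of 50. This rests on the premise that a value in that period is too early to show drug failure, and on such a patient occurring at all.

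Two stronger readings are not supported:
- **That SVR12 is biased.** It is not. The categories apply only after a patient is a non-responder, and the primary rate was the same in every case tried.
- **That the CP with sufficient follow-up (CPSFU) needs the same minimum.** Its second criterion deliberately keeps patients whose last post-baseline value is 50 IU/mL or more, and protocol 9.7.1 says this includes on-treatment values. Removing them would take failures out of a sensitivity denominator and could only raise SVR12. The SAP already excludes patients whose EoT date is missing for reasons unrelated to safety or effectiveness.

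**What to change.** In SAP 4.1.2 and 4.2.7.2.1, define failure to suppress as all on-treatment values at or above 50 IU/mL **and** either
- at least one such value in or after the Week 4 window (study day 15 or later, or a later day that the sponsor justifies in advance), or
- an eCRF stop reason of virological non-response, which SAP 4.2.5 already lists.

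Patients who meet neither condition pass down the existing list. Apply this to both the CP table and its completers' version. State that it refines the protocol definition, as SAP 4.1.1 does for the SVR12 window. Leave the CPSFU definition unchanged.

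A cut-off after the Week 4 window closes (day 43 or later) would go too far without its own justification. It could take patients who stayed at or above 50 IU/mL throughout days 15-42, where the SAP itself assesses response, out of the virologic row.

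The cost is one sentence in each SAP section and one programming condition on dates and reasons already collected. The downside is small: a true non-suppressor sampled only before the chosen day, with no virological stop reason recorded, moves to another category.
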